8.3.6.1. Intervention-emergent ALT/AST Elevations

Management of intervention-emergent ALT/AST elevations is presented graphically in Section 10.6, Appendix 6: Intervention-emergent ALT/AST Elevations, and is described below.

Any intervention-emergent elevation of ALT and/or AST $\geq 3x$ ULN and $\geq 2x$ nadir (ie, lowest value during study participation) should trigger an assessment of confounding factors (alcohol intake, change in concomitant medication, and comorbidities) and should trigger a confirmatory study visit to repeat laboratory testing as specified below. Repeat laboratory values should include AFP, ALT, AST, ALP, bilirubin (total and direct), INR, albumin, HBV DNA, and HDV RNA. Additional tests should be considered based on clinical judgement (refer to Section 10.6, Appendix 6: Intervention-emergent ALT/AST Elevations). The confirmatory visit should be scheduled preferably within 3 days of the receipt of the initial ALT/AST results.

Weekly basis monitoring (or more frequently as long as values increase) until ALT/AST levels have returned to $< 3x$ ULN or $< 2x$ nadir, and if present, liver related symptoms have improved. With ALT and/or AST values $\geq 3x$ ULN and $\geq 2x$ nadir, visit intervals may be extended to 14 days if values have been stable or decreasing on three consecutive visits. The participant will be monitored (laboratory testing of ALT, AST, ALP, bilirubin [total and direct], INR, albumin,

HBV DNA, and HDV RNA) on a weekly basis or more frequently until ALT and/or AST levels have returned to 50% of the maximal value.

Note: In case of urgency, local laboratory assessments could be considered. In case of IWRS participant unblinding and if the investigator requires to be unblinded in case of an emergent safety event (ie, study intervention discontinuation due to ALT flares) to allow further treatment of the participant, a sponsor request can be made to have the investigator and sponsor unblinded to all HDV RNA and HBsAg data from the double-blind phase. Off-treatment local HDV RNA test can be done to exclude/assess for HDV-driven flare.

Management of intervention-emergent ALT and/or AST elevations:

JNJ-3989 treatment should be stopped, and NA treatment needs to be continued in the following situations:

- Participants with liver cirrhosis:
 - Confirmed ALT/AST elevation $>5x$ ULN and $\geq 2x$ nadir
 - ALT/AST elevation $\geq 3x$ ULN and $\geq 2x$ nadir for >4 weeks.
 - If the ALT and/or AST level is $\geq 3x$ ULN and $\geq 2x$ nadir and is associated with any of the following laboratory results or clinical symptoms:
 - INR ≥ 1.5 , OR
 - direct bilirubin $>1.5x$ ULN, OR
 - serum albumin <3.0 g/dL, OR
 - ascites, hepatic encephalopathy, or liver-related symptoms (eg, severe fatigue, nausea, vomiting, right upper quadrant pain in the absence of an alternative medical explanation), OR
 - other indication of reduced liver function.
- Participants without liver cirrhosis:
 - Confirmed ALT/AST elevation $>10x$ ULN and $\geq 2x$ nadir
 - First on-treatment ALT/AST elevation 3 to 5x ULN for >12 weeks
 - Second or following on-treatment ALT/AST elevation 3 to 5x ULN for >4 weeks
 - ALT/AST elevation >5 to 10x ULN for >4 weeks
 - If the ALT and/or AST level is $\geq 3x$ ULN and $\geq 2x$ nadir and is associated with any of the following laboratory results or clinical symptoms:
 - INR ≥ 1.5 , OR
 - direct bilirubin $>1.5x$ ULN, OR
 - serum albumin <3.0 g/dL, OR
 - ascites, hepatic encephalopathy, or liver-related symptoms (eg, severe fatigue, nausea, vomiting, right upper quadrant pain in the absence of an alternative medical explanation), OR

- other indication of reduced liver function.

From Week 52 onwards, results of HBsAg and HDV RNA assessment will be reported to the investigators.

Management of flares observed in the follow-up phase after EOT:

In case of ALT flares that are observed during the follow-up phase, repeat laboratory values should include AFP, ALT, AST, ALP, bilirubin (total and direct), INR, albumin, HBV DNA, and HDV RNA. The participant should be monitored on a weekly basis (or more frequently as long as values increase) until ALT and/or AST levels have returned to $<3x$ ULN or $<2x$ nadir. With ALT and/or AST values $\geq 3x$ ULN and $\geq 2x$ nadir, visit intervals may be extended to 14 days if values have been stable or decreasing on three consecutive visits. For guidance on re-treatment with NA during the follow-up phase, refer to Section 6.5, Re-treatment With NA During the Follow-up Phase.

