- u. Intervention-emergent ALT/AST elevations (ie, ALT and/or AST $\geq 3x$ ULN and $\geq 2x$ nadir [ie, lowest value during study participation]), should trigger an assessment of confounding factors (alcohol intake, change in concomitant medication, and comorbidities) and a confirmatory visit, to be scheduled preferably within 3 days of the receipt of the initial ALT/AST results, to repeat laboratory testing of AFP, ALT, AST, ALP, bilirubin (total and direct), INR, albumin, HBV DNA, and HDV RNA. Note that in case of urgency, local laboratory assessments could be considered (except for HDV RNA and HBsAg to protect the blind). Off-treatment local HDV RNA test can be done to exclude/assess for HDV driven flare. Additional tests should be considered based on clinical judgement. For more details and further management guidance refer to Section 8.3.6.1, Intervention-emergent ALT/AST Elevations and Section 10.6, Appendix 6: Intervention-emergent ALT/AST Elevations.
- v. Urine chemistry sample (quantitative measurement): creatinine, sodium, phosphate, glucose, protein, and albumin. Urinalysis by dipstick: specific gravity, pH, glucose, protein, blood, ketones, bilirubin, urobilinogen, nitrite, leukocyte esterase, and microscopic analysis if needed. In case of a positive dipstick result, a urine sample will be set aside for additional examination of the positive parameter at the central laboratory (eg, quantification as applicable).
- w. Urine sample for selected renal biomarkers including retinol binding protein and beta-2-microglobulin.
- x. A FibroScan assessment will only be done at baseline if it was not done at screening.
- y. Only applicable to participants who are enrolled at a site with access to a FibroScan device.
- z. At Week 52, participants of Arm 2 will switch to JNJ-3989 + NA, therefore, the FibroScan assessment at Week 48 is the baseline assessment for these participants.
- aa. For sites in the US, HDV RNA tests used to determine the participant's eligibility should be performed by a local laboratory.
- bb. HBcrAg and HBV RNA samples may be batched and only selected samples may be tested at the sponsor's discretion. Samples can be used for assessment of other serologic/virologic markers of HBV and HDV.

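### On treatment, a non-cirrhotic participant's ALT or AST above 10x ULN but below twice nadir meets no numeric stop rule and no confirmatory-visit trigger in Section 8.3.6.1 (minor)

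*Protocol*

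**What the plan says.** Section 7.1 makes the ALT/AST list in Section 8.3.6.1 a mandatory reason to discontinue JNJ-3989. The Synopsis repeats the list. For participants without cirrhosis it has five bullets:

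1. "Confirmed ALT/AST elevation $>10x$ ULN and $\geq 2x$ nadir"
2. "First on-treatment ALT/AST elevation 3 to 5x ULN for >12 weeks"
3. A second or later elevation in the same 3 to 5x band, lasting more than 4 weeks.
4. "ALT/AST elevation >5 to 10x ULN for >4 weeks"
5. At least 3x ULN and at least 2x nadir, together with a liver-function abnormality or symptoms.

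The nadir condition is written into bullets 1 and 5 and not into bullets 2 to 4. The corresponding duration bullet for cirrhotic participants does carry it: "ALT/AST elevation $\geq 3x$ ULN and $\geq 2x$ nadir for >4 weeks".

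The Schedule of Activities defines the term itself with the nadir condition: "Intervention-emergent ALT/AST elevations (ie, ALT and/or AST $\geq 3x$ ULN and $\geq 2x$ nadir". Nadir is the lowest value during study participation. That same pair of conditions triggers the extra visit: "The confirmatory visit should be scheduled preferably within 3 days of the receipt of the initial ALT/AST results". Weekly monitoring then runs "until ALT/AST levels have returned to $< 3x$ ULN or $< 2x$ nadir", and a further sentence keeps it going "on a weekly basis or more frequently until ALT and/or AST levels have returned to 50% of the maximal value".

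Inclusion criterion 6.1 requires screening ALT above ULN and below 10x ULN. It sets no limit on AST.

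**The concern.** Above 10x ULN, every numeric condition in the non-cirrhotic list also requires at least twice nadir. When the nadir is itself high, a value can pass 10x ULN without doubling. It then lies above the top duration band, fails the only bullet beyond that band, and does not set off the confirmatory visit.

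In the DAIDS table, ALT at or above 10x ULN is grade 4. Section 2.3.1.2 calls ALT elevation an important potential risk of JNJ-3989 and suspects a causal relationship. In Part 1, 12 of 22 participants had on-treatment ALT elevations up to Week 48, 7 of them grade 4. A mandatory stopping list for that risk should not be silent on a grade 4 value, nor treat a higher value more leniently than a lower one.

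**Working it through.** There is no stated figure to reproduce; the check is on the threshold logic.

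**Inputs.** Let N be the nadir and v the current value of one enzyme, both in multiples of ULN. I assume each enzyme is compared with its own nadir, and that screening counts as study participation.

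- Bullet 1: v > 10 and v ≥ 2N.
- Bullets 2 and 3: 3 ≤ v ≤ 5, with durations.
- Bullet 4: 5 < v ≤ 10 for more than 4 weeks.
- Bullet 5 and the confirmatory-visit trigger: v ≥ 3 and v ≥ 2N.

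**Uncovered range.** For v > 10, bullets 2 to 4 cannot apply, and bullets 1 and 5 and the trigger all need v ≥ 2N. So nothing applies when 10 < v < 2N. This range is non-empty only if 2N > 10, that is, N > 5.

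| Nadir (x ULN) | 2 × nadir | Range with no bullet and no trigger (x ULN) |
|---|---|---|
| 5 | 10 | none |
| 6 | 12 | above 10 to below 12 |
| 7 | 14 | above 10 to below 14 |
| 9 | 18 | above 10 to below 18 |

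Enumerating the rules in steps of 0.1x ULN gave the same region: nadirs 5.1 to 9.9, values 10.1 to 19.7, and no gap at nadir 5 or below.

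**Ceiling.** Criterion 6.1 puts screening ALT below 10x ULN, so for ALT N < 10 and 2N < 20. AST has no entry cap there, so the below-20x limit does not carry over to AST.

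**Both enzymes.** The trigger is met by ALT and/or AST. If the other enzyme meets it, the confirmatory visit applies, so the ranges above are upper bounds.

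**Ordering.** Suppose bullet 4 carries no nadir condition and N = 7, so 2N = 14. A value of 9.9 for 5 weeks meets bullet 4 and stops treatment. A value of 13 is above 10 and below 14, so it meets no bullet. If bullet 4 does carry the condition, 9.9 < 14 fails as well: the reversal disappears, but 13x still has no trigger.

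**Timing.** With the trigger, the repeat is preferably within 3 days of the result. Under Section 8.2.4, if the investigator judges the grade 3 or 4 value clinically significant, it is no later than 72 hours after the result. Otherwise it is the next scheduled chemistry: Day 701 − Day 673 = 28 days, or 28 ± 14 = 14 to 42 days with both ±7-day windows at their extremes.

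**Who can be there.** The nadir can only fall, so one ALT at or below 5x ULN closes the ALT gap for good. Scheduled chemistry up to Week 52 is screening, Week 0, Week 2, the twelve 4-weekly visits from Week 4 to Week 48, and Week 52: 3 + 12 + 1 = 16 readings, all of which must exceed 5x ULN.

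**The case against.** The strongest reply is that the nadir multiple is deliberate. Participants enter with raised ALT, and a relative threshold separates new injury from background disease. Amendment 3 tightened it from 3x to 2x nadir, and the safety-management changes in that amendment were made in consultation with the IDMC. This stands as a reason to keep the stop rule relative. It does not explain why a grade 4 value should lack even an automatic repeat.

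A second reply is that safeguards remain. Besides the Section 8.2.4 repeat, Section 7.1 has investigator-judgement and decompensation stops, Section 2.3.3 requires discontinuation when liver function is decreasing, the DRC monitors ALT flares and the IFLEP adjudicates them. A participant who met the trigger earlier also stays monitored until values fall to half the peak. A reader might therefore infer from the gap that a grade 4 ALT goes without follow-up; the documents do not support that. These routes rest on judgement, on other findings or on periodic review, and none sets an ALT threshold for this range.

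Third, the section title, the definition in the Schedule of Activities and the Amendment 3 onset threshold all favour reading the nadir condition into the duration bullets. That makes the uneven wording, taken alone, a matter of clarification. It does not close the gap, which exists on either reading.

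Fourth, the Appendix 6 flow chart is not visible in the text at hand and may settle the reading. Section 7.1 points to Section 8.3.6.1, however, and Appendix 6 refers back to it, so the figure would not clearly override the text.

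**Conclusion.** The gap is real and minor. On treatment, for a non-cirrhotic participant whose every ALT has been above 5x ULN, an ALT above 10x ULN and below twice nadir has no automatic numeric action in Section 8.3.6.1 or the Synopsis, unless AST meets the trigger. The same applies to AST against its own nadir, without the 20x ceiling. If the duration bullets carry no nadir condition, the list is also not monotone.

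A reader might infer a material exposure from the Part 1 flare rate; the documents do not support that. At Amendment 5, Part 1 treatment was complete and 17 Part 2 participants had entered the open-label phase, with treatment ending at Week 96 (Arm 1) or Week 100 (Arm 2), or at the next planned visit if later. Remaining above 5x ULN at 16 scheduled readings is unlikely. Read literally, bullet 4 would also have stopped JNJ-3989 in anyone who stayed above 5x and up to 10x ULN for more than 4 weeks. Very few, possibly none, are likely to be affected; the number with such a nadir is not given. All participants are past the double-blind phase, so the Week 48 result does not change.

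**What to change.** In Section 8.3.6.1 and the Synopsis:

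1. State that any on-treatment ALT or AST above 10x ULN triggers the existing confirmatory visit regardless of nadir. If confirmed, the existing weekly monitoring follows, with a documented stop-or-continue decision agreed with the sponsor. Monitoring should run until the value is at or below 10x ULN, with the existing 14-day extension. A separate end rule is needed because falling below twice nadir, one of the current end points, is already satisfied in this range.
2. State whether the nadir condition applies to the three non-cirrhotic duration bullets, consistent with Appendix 6. If it does not, change the top band from above 5x up to 10x ULN to simply above 5x ULN for more than 4 weeks, so that a higher value is never treated more leniently.

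With item 1, every value in 10 < v < 2N gets a confirmatory visit, and the relative-to-nadir condition in the above-10x stop bullet stays intact.

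The cost is wording, by amendment or clarification letter. For the very few affected, it is one confirmatory visit plus 4 − 1 = 3 extra visits per 4-week interval, falling to 2 − 1 = 1 once the 14-day extension applies.

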8.3.6.2. Rash

Participants should be informed that they should contact their doctor immediately when they notice any generalized skin reaction. This skin reaction should be evaluated in the clinic the same day (if possible) or the next day.

All rash events should be captured in the AE section of the CRF. A separate Rash page will be completed in case of a rash event.

Monitoring of the evolution of rash events will be performed as described in Table 3 in Section 10.5, Appendix 5: Rash Management.

When safety blood samples are drawn as per the rash management guidelines, these should be processed by the local laboratory. The following parameters will need to be tested: AST, ALT, sedimentation rate, complete blood cell count (including hemoglobin, hematocrit, red blood cell [RBC] count, white blood cell [WBC] count, differential count [neutrophils, lymphocytes, monocytes, eosinophils, and basophils], and platelet count), and creatinine. Relevant laboratory assessment values are to be shared with the sponsor (if applicable and local regulations allow) as per the “Instructions for Investigators for sharing of Digital Pictures and Local lab reports” and should be de-identified.

The participant may be treated symptomatically until the rash resolves. Oral antihistamines (eg, cetirizine, levocetirizine) and/or topical corticosteroids may provide symptomatic relief but effectiveness of these measures has not been established. If systemic corticosteroids exceeding 5 mg of prednisolone equivalent/day are required for treatment of rash, the study intervention needs to be permanently discontinued. If the rash is considered to be most likely due to concomitant illness or non-study drugs, standard management, including discontinuation of the likely causative agent, should be undertaken.

Injection Site Reactions

At the time points specified in the [Schedule of Activities](#) or at an unscheduled visit if needed, an evaluation of the injection site will be performed based on participant's description and/or physical examination. Evaluation will include at a minimum the time of occurrence, time of resolution and a description of the abnormality including its maximal diameter. For each ISR, information on pain, erythema, induration and pruritus should be obtained as specified in the DAIDS scale (see Section 10.9, Appendix 9: DAIDS Table).

All ISRs (including ISRs below grade 1) will need to be recorded in the special events section of the CRF.

Digital pictures will be taken when considered appropriate; all efforts should be made to collect images in case of grade 3 and 4 ISRs. Digital pictures will only be taken and collected from participants who consent separately to this component of the study. If digital pictures are required, they should be de-identified and provided to the sponsor.

